6.1.1 Single Oral Dose, Three-Way Cross-Over

32 healthy male or female participants will be enrolled in 1 of 6 single-dose, three-way cross-over sequences (designated as 1 through 6, respectively) in an ascending fashion. Sequences 1, 3, 4, and 5 will have 5 participants each, and Sequences 2 and 6 will have 6 participants each.

Each sequence will proceed through three cross-overs (suspension-fasted, tablet-fed, tablet-fasted) according to the schematic above, with dosing to occur on Day 1 of each of the three Periods. Participants in the fasted portion of each sequence will be dosed under overnight fasted conditions and will remain fasted for 4 hours post-dose. Water consumption is permitted as desired except for 1 hour before and after administration of Study Drug.

To assess the effect of food on CVN424 bioavailability in tablet formulation, the single-dose administration will be administered after ingestion of a standardized high-fat, high-calorie meal according to FDA Guidance for Industry (Food-effect bioavailability and fed bioequivalence studies, Jun 2022).

Participants for all sequences will be admitted to the study unit 1 day prior to dosing and remain in the unit for safety and PK assessments through 96 hours post-dose. The total confinement for each period will be 5 nights per sequence (15 days total) unless extended at the discretion of the Investigator, e.g., for monitoring and/or management of AEs.

Page 22 of 64 30 Aug 2022

Once 96-hour post-dose PK has been collected, participants will be discharged from the clinical research unit (CRU) for the remainder of the washout period and return the day prior to their next dose.

An outline of the study visit schedule is included in Appendix A.

6.2 Justification for Study Design, Dose, and Endpoints

This is a randomized, open-label, single-oral dose, three-way crossover study under fasted and fed conditions in healthy participants. The selected dose level (150 mg) is expected to provide a high level of GPR6 occupancy in brain tissue even at its steady-state nadir plasma concentration.

Based on the Phase 2 data (see Section 4.1) and a previous healthy volunteer study, the planned dose of CVN424 is within the dose range previously shown to be safe and well-tolerated.

AEs, physical exams, vital signs and weight, ECG findings, and clinical laboratory results are used as safety assessments to determine the relative bioavailability of the CVN424 suspension and tablet formulations. The plasma PK parameters will further elucidate the pharmacology of CVN424 in the intended participant population.

6.3 Premature Termination or Suspension of Study or Investigational Site

6.3.1 Criteria for Premature Termination or Suspension of the Study

The study will be completed as planned unless new information or other evaluation regarding the safety of the study medication indicates an adverse change in the risk profile for the compound, such that the Sponsor or Institutional Review Board (IRB) considers the risk is no longer acceptable for participants participating in the study.

6.3.2 Criteria for Premature Termination or Suspension of Investigational Sites

A study site may be terminated prematurely or suspended if the site (including the Investigator) is found in significant violation of Good Clinical Practice (GCP), protocol, or contractual agreement and is unable to ensure adequate study performance or otherwise permitted by the contractual agreement.

If the Sponsor, IRB, or regulatory authority elects to terminate or suspend the trial or the participation of an investigational site, a trial-specific procedure for early termination or suspension will be provided by the Sponsor; applicable investigational sites will follow the procedure during termination or trial suspension.

6.3.3 Procedures for Premature Termination or Suspension of the Study or the Participation of Investigational Site(s)

If the Sponsor, IRB, or regulatory authority elects to terminate or suspend the study or the participation of an investigational site, a study-specific procedure for early termination or suspension will be provided by the Sponsor; applicable investigational sites will follow the procedure during the course of termination or study suspension.

7.0 PARTICIPANT POPULATION

Screening for eligible participants will be performed within 28 days prior to randomization.

7.1 Inclusion Criteria

Participant eligibility is determined according to the following criteria prior to entry into the study:

- 1. In the Investigator's opinion, the participant can understand and sign the Informed Consent Form (ICF) and comply with all protocol requirements.
- 2. The participant is male or female adult who is 18 to 55 years of age, inclusive at the time of Screening.
- 3. Participant weighs at least 45 kilograms (kg) (99 pounds [lbs]) and has a BMI between 18.0 and 35.0 kg/m2, inclusive at Screening.
- 4. The participant is medically healthy with no clinically significant (CS) or relevant abnormalities in medical history, physical exam, vital signs, ECG, and laboratory evaluations (hematology, chemistry, and urinalysis) as assessed by the Investigator.
- 5. Female participants of childbearing potential and male participants with female partners of childbearing potential must agree to either remain abstinent or use two methods of adequate and reliable contraception (see Section 9.1.12) throughout the study and at least 12 weeks after the last dose of study drug has been taken.

7.2 Exclusion Criteria

Any participant who meets any of the following criteria will not qualify for entry into the study:

- 1. Vegetarian, Vegan, Lactose intolerant, or follows a Kosher diet.
- 2. Evidence of clinically significant neurologic or other disorder or impairment that, in the opinion of the Investigator, is reasonably expected to impact the ability of the participant to participate or confound the study results.
- 3. A current or recent (within 6 months) gastrointestinal disease that would be expected to influence the absorption of drugs (i.e., a history of malabsorption, any surgical intervention known to impact absorption [e.g., bariatric surgery or bowel resection]). Note, history of cholecystectomy is permitted if there is no evidence of malabsorption per the Investigator.
- 4. A history of cancer or other malignancy, with the exception of low-grade cervical intraepithelial neoplasia, low-grade (low-risk) prostate cancer, or 5-year cancer-free survivors of basal or squamous cell carcinoma or higher-grade cervical intraepithelial neoplasia or prostate cancer.
- 5. A positive test result for hepatitis B surface antigen (HBsAg), hepatitis C virus (HCV) antibody, or a human immunodeficiency virus (HIV) infection at Screening.
- 6. Any clinically significant abnormalities in labs: biochemistry (including liver function test [LFT], estimated glomerular filtration rate [eGFR], and glucose), standard

- hematology with white blood cell (WBC) differential, c-reactive protein (CRP), coagulation tests, lipase, amylase, albumin, and calcium.
- 7. A supine blood pressure outside the ranges of 80 to 160 mm Hg for systolic and 50 to 100 mm Hg for diastolic, confirmed with up to two repeat tests at the Screening Visit; or symptomatic orthostatic hypotension, in the opinion of the Investigator.
- 8. A resting heart rate outside the range of 40 to 100 beats per minute (bpm) confirmed with up to two repeat tests at the Screening Visit. Note that 40-50 and 90-100 bpm may be permitted only at the discretion of the Investigator.
- 9. Positive urine result for illegal drugs at Screening and Check-In, or history of illicit drug use or alcohol abuse within 1 year prior to the Screening Visit.
- 10. Received any investigational compound (defined as a drug that has not been FDA-approved) within 30 days prior to the first dose of study medication or within 5 half-lives of the investigational compound, whichever is greater.
- 11. Within 14 or 28 days prior to randomization, ingested any of the following excluded medication, supplements, or food products: St. John's wort, ginseng, kava, Ginkgo biloba, Chinese herbs, and melatonin, or known strong inhibitors/inducers of cytochrome P-4503A4/5, including rifampin, clarithromycin, ketoconazole, itraconazole. For full list of prohibited medications and dietary products, (See Table 2).
- 12. Regularly uses nicotine-containing products (including but not limited to cigarettes, electronic cigarettes, pipes, cigars, chewing tobacco, nicotine patch, or nicotine gum). The casual users (≤ 10 cigarettes/week) may participate; however, they must agree to refrain from 30 days before Day 0 (Inpatient Check-in) for the duration of the study or a positive urine cotinine test at Inpatient Check-in.
- 13. Known history of coronary artery disease and hospitalization for myocardial infraction, ischemic heart disease, or congestive heart failure within the 2 years prior to the screening visit.
- 14. Any clinically significant medical, psychiatric, or laboratory abnormality that, in the judgment of the Investigator, is likely to interfere with study participation
- 15. A history of major depression or risk of suicide according to the Investigator's clinical judgment or has made a suicide attempt.
- 16. Is a study site employee or an immediate family member of a study site employee.

Table 2 Prohibited Medication and Dietary Products

Use of the agents in Table 2 (prescription or nonprescription) is prohibited from the time points specified until completion of all study activities.

The following table defines the prohibited medications and dietary products:

Prohibited Medication and Dietary Product

Within 30 days before Randomization:

• Nicotine-containing products

Within 28 days before Randomization:

- St. John's wort, ginseng, kava, ginkgo biloba, Chinese herbs, and melatonin
- Known strong inducers of cytochrome P-4503A4/5 or p-gp, including rifampin
- Immunization vaccines: Inclusive of but not limited to H1N1 and flu vaccinations. Participants who have received the COVID-19 Vaccine between -10 and -28 days may participate, provided they did not experience any side effects of any description. COVID-19 vaccine doses may be administered 7 days post-study medication dosing.

Within 14 days before Randomization:

- Known strong inhibitors of cytochrome P-4503A4/5, including clarithromycin, ketoconazole, itraconazole
- All prescription and non-prescription medications, herbal remedies, or vitamin supplements. Medication listed as part of acceptable birth control (Section 9.1.12), hormone replacement therapy, and thyroid hormone replacement therapy medication will be allowed without dose changes during the study.

Potential exceptions:

- Occasional use of acetaminophen (~1 g/day) and 400mg ibuprofen TDS when required or other medication as approved by the Sponsor's Medical Monitor on a case-by-case basis is allowed except on Day 1
- Certain prescription medications may be allowed on a case-by-case basis at the discretion of the Investigator and Sponsor

Page 26 of 64 30 Aug 2022

7.3 Diet, Fluid, and Activity Control

Participants will refrain from the consumption of food and beverages containing the following:

- Xanthines/caffeine: 24 hours prior to each dosing and until last PK sample in each period (small amounts of caffeine derived from normal foodstuffs, e.g., 250 mL/8 oz/1 cup decaffeinated coffee or other decaffeinated beverage per day, except for espresso; 45 g/1.5 oz chocolate bar, per day, would not be considered a deviation to this restriction).
- Alcohol: 48 hours prior to each dosing and until last PK sample in each period.
- Grapefruit/Seville orange: 14 days prior to first dosing and until the last pk sample in Period 3.

Participants will be confined to the clinic on three separate sequences for approximately 5 days which will allow dosing sufficient time to collect additional post-dose PK samples and monitor for safety and tolerability (Check-in through Day 5 for each of the three Periods). During confinement, with the exception of the dosing day (See Section 7.3.1), participants will be provided 3 standard meals and a snack per day, each containing approximately 30% fat (relative to the total calories). Each meal and/or snacks served at the CRU will be standardized, similar in caloric content and composition, and taken at approximately the same time in each period. When confined, standard meals and snacks will be provided at appropriate times, except when they are required to fast. When confined in the CRU, participants will be required to fast from all food and drink except water between meals and snacks.

The study menu should be recorded and submitted to the study file, with a copy provided to the Sponsor following treatment. Other fluids may be given as part of meals and snacks but will be restricted at all other times throughout the confinement period.

If a blood draw or any study procedure coincides with a meal, the blood draw will take precedence, followed by the study procedure and then the meal.

Participants will remain in bed at a semi-supine position for 4 hours following the dose administration, except as necessitated by an AE or study procedures (e.g., obtaining a 12-lead ECG). Participants must refrain from strenuous exercise for 72 hours before Inpatient Check-in and until check-out.

7.3.1 On Dosing Days:

For the Suspension (fasted) and Tablet (fasted) portions: Breakfast will not be provided on dosing days. Participants must fast for a minimum of 4 hours after dose administration unless otherwise indicated. CVN424 will be administered with approximately 240 mL of water after a fast of at least 10 hours. Participants will continue to fast for an additional 4 hours after dosing and eat lunch following the 4-hour PK blood collection. Participants may consume water ad libitum except for 1 hour before and 1 hour after drug administration.

For the Tablet (fed) portion (food effect): CVN424 will be administered after ingesting a standardized high-fat, high-calorie meal according to FDA Guidance for Industry (Food-effect

bioavailability and fed bioequivalence studies, June 2022). Participants will finish their breakfast in its entirety within 30 minutes and will receive an investigational product 30 minutes (±5 minutes) after beginning the meal. The meal start and stop times, and percentage of the meal consumed will be recorded in the source, and the appropriate electronic case report form (eCRF) for all meals served on dosing days.

7.4 Criteria for Discontinuation or Withdrawal of a Participant

Participants are free to withdraw from the study at any time upon request. The Investigator may remove a participant from the study if, in the Investigator's opinion, it is not in the best interest of the participant to continue the study. Participants may be discontinued due to the following (not inclusive):

- 1. The participant has experienced an AE that requires early termination because continued participation imposes an unacceptable risk to the participant's health, or the participant is unwilling to continue because of the AE.
- 2. Liver Function Test (LFT) Abnormalities

Study medication should be discontinued immediately with appropriate clinical follow-up (including repeat laboratory tests until a participant's laboratory profile has returned to normal/baseline status) if the following circumstances occur at any time during study medication treatment:

- Alanine aminotransferase (ALT) or aspartate aminotransferase (AST) >8 × upper limit of normal (ULN), or
- ALT or AST >5 × ULN and persists for more than 2 weeks, or
- ALT or AST >3 × ULN in conjunction with elevated total bilirubin >2 × ULN or INR >1.5, or
- ALT or AST >3 × ULN with appearance of fatigue, nausea, vomiting, right upper quadrant pain or tenderness, fever, rash and/or eosinophilia (>5%).
- 3. Significant protocol deviation. The discovery post-randomization that the participant failed to meet protocol entry criteria or did not adhere to protocol requirements and continued participation poses an unacceptable risk to the participant's health.
- 4. Lost to follow-up. The participant did not return to the clinic and attempts to contact the participant were unsuccessful. Attempts to reach the participant must be documented.
- 5. Voluntary withdrawal. The participant (or participant's legally acceptable representative) wishes to withdraw from the study. The reason for withdrawal, if provided, should be recorded in the eCRF.
 - Note: Attempts should be made to determine the underlying reason for the withdrawal and, where possible, the primary underlying reason should be recorded (e.g., withdrawal due to an AE; withdrawal due to relocation).
- 6. The Sponsor, IRB, or regulatory agency terminates the study.
- 7. Other.

Page 28 of 64 30 Aug 2022

The primary reason for discontinuation or withdrawal of the participant from the study or study medication should be recorded in the eCRF using the following categories. For screen failure participants, refer to Section 9.1.14.

Note: The specific reasons should be recorded in the "specify" field of the eCRF.

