- Alanine aminotransferase (ALT) or aspartate aminotransferase (AST) >8 × upper limit of normal (ULN), or
- ALT or AST >5 × ULN and persists for more than 2 weeks, or
- ALT or AST >3 × ULN in conjunction with elevated total bilirubin >2 × ULN or INR >1.5, or
- ALT or AST >3 x ULN with appearance of fatigue, nausea, vomiting, right upper quadrant

pain or tenderness, fever, rash and/or eosinophilia (>5%)

the event should be recorded as an SAE (note the reason for Seriousness: medically important event) and reported as per Section 9.7.2. The Investigator must refer to section 7.4 Criteria for Discontinuation or Withdrawal of a Participant for guidance as to the appropriate next steps.

Signed,

Cerevance

NOTE TO FILE

To: Cerevance 424-102 Study Trial Master File

From: Consultant to Cerevance

Date: 30Sep2022

Study: CVN424-102

Re: Protocol Clarifications

The following are clarifications for the CVN424-102 protocol version 1.0 dated 30Aug2022.

- Randomization: clarifying that Celerion will serve as designee for the randomization generation
- Physical Assessment at follow-up visit: clarifying that this is to be a symptom driven physical examination
- · Vital signs: clarifying that temperature is not needed in triplicate
- Appendix A: Schedule of Study Procedures
 - o Follow-Up:
 - Overall Study Day # to be update to 42
 - Randomization:
 - To be moved from first Check-in to first Dosing day
 - Pregnancy Test:
 - Add assessment to Day 5 of Period 3
 - C-SSRS:
 - Remove assessment from Day 1 of Periods 2 and 3 as well as from Follow-Up visit
 - o Physical Examination:
 - Add assessment to Day 2 of each Period for 24-hours post-dose
 - Vital Signs (footnote 3):
 - Update to include Respirations
 - Respirations should also be added to the Study Summary (page 11)
 - Urinalysis (footnote 5)
 - Update to include statement that Predose labs do not need to be reviewed prior to dosing
 - Clinical laboratory tests (footnote 7):
 - Partial list should be removed as Table 4 in section 9.1.11 indicates the full list of tests
 - ECG (footnote 11):
 - Study days to be updated to 0, 14, and 28
 - 3 hours post-dose window to be updated to +/- 30 minutes

Signed,

CVN424-102; CA38736; 16.1.1 Protocol and Protocol Amendments

Page 1 of 64 30 Aug 2022

PROTOCOL

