Participants for all sequences will be admitted to the study unit 1 day prior to dosing and remain in the unit for safety and pharmacokinetics (PK) assessments through 96 hours post-dose. The total confinement period will be 5 nights for each period unless extended at the discretion of the Investigator, e.g., for monitoring and/or management of adverse events (AEs).

Once 96-hour post-dose PK has been collected, participants will be discharged from the unit for the remainder of the washout period and return the day prior to their next scheduled dosing period.

Primary Objective:

To determine the relative bioavailability of 150 milligrams (mg) of CVN424 administered in a single dose of suspension formulation compared to 150 mg tablet.

Secondary Objectives:

To establish the effects of food on the rate and extent of absorption of CVN424 150 mg tablet when administered in fed conditions compared to administration under fasting conditions.

To assess the tablet's safety under fast and fed conditions and suspension under fasted conditions.

Exploratory Objectives:

To explore serum/plasma (e.g., potential characterization of drug metabolites) that may contribute to variability in CVN424.

To assess urine concentrations and volumes to enable calculation of urine PK parameters where possible.

Participant Population:

Healthy male and female participants 18 to 55 years old (inclusive)

Number of Participants:	Number of Sites:	
Estimated total: 32 participants (4 sequences of 5 and 2 sequences of 6)	1 (United States)	
Dose Level(s):	Route of Administration:	
Participants to receive a single-dose level of 150 mg CVN424 in either tablet or suspension formulation	Oral	
Duration of Treatment:	Period of Evaluation:	
Single oral dose on Day 1 of Periods 1, 2, & 3 (Study Days 0, 14,	Screening Period: up to 28 days	
& 28)	• 5 days of inpatient confinement from Check-In until after the 96-hour post-dose blood draw on Day 5	
	• 9 additional days of washout (Days 6-13)	
	To be repeated for the subsequent two Periods	
	Total Duration: Approximately 10 weeks	

Main Criteria for Inclusion:

Healthy male and female participants, 18 to 55 years of age, inclusive, and have a body mass index (BMI) between 18.0 and 35 kg/m² inclusive at Screening.

A complete list of inclusion criteria is provided in Section 7.1.

Main Criteria for Exclusion:

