9.7 Procedures

9.7.1 Collection and Reporting of AEs

9.7.1.1 AE Collection Period

Collection of AEs will commence from the time the participant signs the informed consent to participate in the study and continue until 14 days following last dose.

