Appendix A: Schedule of Study Procedures

Overall Study Day #	-28 to -2	-1	0	1-4	5-12	13	14	15-18	19-26	27	28	29-32	33 +/- 2
Period				1			2				3	3	
Day		0	1	2-5	6-13	14	1	2-5	6-13	14	1	2-5	15 +/- 2
					Washo	ut			Washout				
			Inpati	ent	ent		Inpatient				Inpatient		
	Screening	Check- in	Dosing			Check-in	Dosing Day			Check-in	Dosing		Follow- Up/ET¹
Informed Consent	X												
Inclusion/Exclusion Criteria	X												
Review ICF and I/E	X	X				X				X			
Demographics and Medical History	X												
Randomization ²		X											
Concomitant medications	X	X	X	X		X	X	X		X	X	X	X
Participant Admission to CRU		X				X				X			
Vital signs ³	X	X	X	X		X	X	X		X	X	X	X
Weight, height, and BMI ⁴	X												X
Urinalysis ⁵	X		X	X			X	X			X	X	X
Urine Drug Screen	X	X				X	_			X	_	_	
Cotinine Screen		X				X				X			

¹ Assessments to be completed on final in-patient day and will be repeated if AE requires in-person follow-up

² Once eligibility has been confirmed by Screening assessments ³ Assessments to include HR, BP, and temperature

⁴ Height only at screening ⁵ Part of safety assessments (Pre and 24h post-dose)

Page 62 of 64 30 Aug 2022

Physical Examination ⁶	X		X			X			X		X
Hepatitis panel and HIV antibody test	X										
Clinical laboratory tests ⁷	X	X	X	X		X	X		X	X	X
Pregnancy Test ⁸	X	X		X	X		X	X			X
FSH ⁹	X										
C-SSRS ¹⁰	X	X		X	X	X	X	X	X	X	X
ECG ¹¹	X		X			X			X		X
PK Blood Collection ¹²			X	X		X	X		X	X	
PK Urine ¹³			X	X		X	X		X	X	
Overnight Fasting		X ¹⁴			X^{15}			X^{16}			
CVN424 Dosing ¹⁷			X			X			X		
AE Assessment		X	X	X	X	X	X	X	X	X	X

⁶ Full PE at Screening, Medical Assessment pre-dose (within 24 hours prior to dosing) and 24-hours post-dose

⁷ Pre and Post dose Safety Labs, standard hematology with WBC differential, CRP, coagulation tests, lipase, amylase, albumin, and calcium. Predose labs do not need to be reviewed prior to dosing. Post dose to be done at 48 hours and EOT. Unscheduled as clinically indicated.

⁸ Serum pregnancy test at Screening and urine pregnancy test at subsequent discharge and check-ins

⁹ FSH level will be obtained on post-menopausal women (defined as continuous amenorrhea of at least 2 years and not surgically sterile)

¹⁰ Screening, Check-in, 24 and 96-hour post dose

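### With doses 14 days apart, the >5 × ULN liver limb that needs more than 2 weeks' persistence cannot be met before the immediately following dose, nor by Day 42 if the elevation arises after dose 3

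*Protocol*

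**What the plan says.** Protocol Section 7.4 lists four liver findings that require immediate discontinuation "if the following circumstances occur at any time during study medication treatment". The second reads "ALT or AST >5 × ULN and persists for more than 2 weeks, or". The other three have no 14-day requirement: a value above 8 × ULN; a value above 3 × ULN with raised bilirubin or INR; and a value above 3 × ULN with listed symptoms, rash or eosinophilia. Section 7.5 makes discontinuation mandatory once a 7.4 criterion is met.

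The Note to File of 20 October 2022 replaces Section 9.7.3 and repeats the four findings as SAE criteria: "the event should be recorded as an SAE (note the reason for Seriousness: medically important event".

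The Study Summary gives the dosing as "Single oral dose on Day 1 of Periods 1, 2, & 3 (Study Days 0, 14", with Day 28 following. The Note to File of 30 September 2022 corrects the ECG days to match ("Study days to be updated to 0, 14, and 28") and moves follow-up: "Overall Study Day # to be update to 42". Appendix A footnote 7 sets the safety panels: "Post dose to be done at 48 hours and EOT". It adds that predose results need not be looked at before the dose is given. SAP Section 7.5 also lists a chemistry panel on Day 2 of each period, about 24 hours after dosing. AE collection runs from consent and will "continue until 14 days following last dose" (Section 9.7.1.1). Section 9.7.2 uses the same period for SAEs.

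**The concern.** A persistence criterion can protect a participant from a further dose only if the persistence can be established before that dose. Here the required duration is longer than the gap between doses. A participant with ALT or AST between 5 and 8 × ULN, no symptoms, and normal bilirubin and INR meets none of the other three limbs. For that participant the only mandatory limb that could apply cannot be satisfied until after the next exposure.

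The 20 October note carries the mismatch into SAE reporting. After the last dose the collection window is 14 days, and the criterion needs more than 14. What is at stake is participant safety and the completeness of SAE classification.

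**Working it through.** **Inputs.** Doses on Study Days 0, 14 and 28 (Study Summary, Appendix A, 30 September note). Required persistence: more than 14 days (Section 7.4). First post-dose panel: 48 h (Appendix A footnote 7) or about 24 h (SAP Section 7.5). Last inpatient panel: 96 h (SAP Section 7.5). Collection ends 14 days after the last dose (Section 9.7.1.1).

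**1. The plan's own figures.** Dose interval: 14 − 0 = 28 − 14 = 14 days. End of collection: 28 + 14 = Day 42, which agrees with the follow-up day in the 30 September note.

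**2. Time available before the next dose.** An elevation present from day t meets the limb only after day t + 14. If it arises after a dose on day d, then t ≥ d, so the limb is met only after d + 14, which is the next dosing day. Counted from the first panel, the time available is 14 − 2 = 12 days (48 h) or 14 − 1 = 13 days (24 h).

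**3. All three periods.**

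| Arises in | Present from (Study Day) | Met only after (Study Day) | Before the next dose? | Before any later dose? | By Day 42? |
|---|---|---|---|---|---|
| Period 1 | 0 / 2 / 4 | 14 / 16 / 18 | No (dose 2, Day 14) | Yes (dose 3, Day 28) | Yes |
| Period 2 | 14 / 16 / 18 | 28 / 30 / 32 | No (dose 3, Day 28) | None left | Yes |
| Period 3 | 28 / 30 / 32 | 42 / 44 / 46 | No dose left | None left | No |

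The three values in each cell are onset at dosing, first seen at 48 h and first seen at 96 h. With a 24-h panel after dose 3 (Day 29), the limb is met only after 29 + 14 = Day 43.

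**4. Can scheduled panels show it?** For Period 1, Day 2 to Day 18 is 16 days, so yes, before dose 3. For Period 2, Day 16 to Day 32 is 16 days, so yes, inside Days 28 to 42. An elevation first seen on Day 4 is exactly 14 days old on Day 18. On scheduled panels alone it would be documented only around the Day 28 dose, although repeat tests under Section 9.1.11 could show it sooner. For Period 3 the last scheduled panel is Day 32, four days after the dose. Routine follow-up is by telephone (Section 9.3.7).

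**5. The other reading of the washout.** Section 9.3.4 describes a 14-day washout after the 96-hour draw. Taken literally, doses are 4 + 14 = 18 days apart (Days 0, 18, 36). An elevation seen at 48 h would then qualify after Day 16, before the Day 18 dose; one first seen at 96 h would qualify only after Day 18, so not before it. After dose 3 nothing changes: collection ends on 36 + 14 = Day 50, and the limb is met only after Day 50 at the earliest.

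**The case against.** The strongest reply is that Section 7.4 applies throughout treatment, and nothing says this limb was meant to block the very next dose. It is one of four, and the other three can act without a 14-day wait. Other text also reaches the participant described above:

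- Appendix A has eligibility reviewed again at each check-in. Exclusion 6 covers clinically significant liver test abnormalities, and Section 12.2 allows no exemptions.
- The 20 October note makes any ALT or AST above 2 × ULN an AE, so item 1 of Section 7.4 (an AE posing unacceptable risk) can apply.
- Section 9.1.11 calls for a retest within 7 days of a value above 3 × ULN, and for Medical Monitor contact if it stays there.
- AEs are followed until laboratory changes return to baseline or are explained (Section 9.7.1.2).
- A related SAE reported spontaneously after the window still goes to the sponsor (Section 9.7.2).

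After dose 3 there is no dose left to stop, so only SAE classification is affected. Follow-up at 14 ± 2 days can also fall as late as Day 44.

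Much of this stands. A reader might infer that such a participant simply stays eligible, or that Medical Monitor discussion is the only recourse; the passages above do not support that. They do, however, turn on judgements of clinical significance or risk. The eligibility items are written as entry criteria, and footnote 7 removes review of the predose panel as a required step. None of them makes the mandatory limb operate in time.

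**Conclusion.** The point holds in limited form. On the Day 0/14/28 schedule, an elevation arising after a dose cannot meet the limb before the immediately following dose: at most 14 days are available, or 12 to 13 from the first panel, against more than 14 required. For an elevation arising after dose 3, the SAE copy cannot be met by Day 42; from the first panel it is met only after Day 43 or 44, which is 1 to 2 days past closure.

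Two stronger readings are tempting and wrong. One is that the limb can never operate in this study; a Period 1 elevation can meet it before dose 3. The other is that it cannot be met anywhere in the 14 days after the last dose; a Period 2 elevation can meet it there, and the collection period is in any case continuous from consent.

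The result assumes that doses fall on the scheduled days and that the elevation was absent before the dose in question. The next-dose part depends on 14-day spacing, which Section 9.3.4 puts in doubt. The post-dose-3 part does not. The documents give no rate for such elevations, and I assume they are rare. The PK comparisons are unaffected. This should be corrected for safety reasons, but it does not threaten the trial's conclusions.

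**What to change.** Reconcile the persistence limb in Section 7.4, and its copy in the 20 October 2022 note, with:

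- the dosing interval in the Study Summary and Appendix A, and the conflicting washout wording in Section 9.3.4;
- Appendix A footnote 7, on review of predose laboratory results;
- the 14-day AE/SAE collection period in Sections 9.7.1.1 and 9.7.2.

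The threshold, the duration and the handling of a case still unresolved when collection closes are the sponsor's decisions; none is proposed here.

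The direct cost is wording. Depending on what the sponsor chooses, a dose might occasionally be withheld, which would leave that participant without PK data for a period. The plan enrolls 32 to secure 28 evaluable participants, so it already allows for 32 − 28 = 4 losses.
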